## 14.3 Appendix 3: Bayesian Cox proportional hazards model with meta-analytic-predictive prior and operating characteristics of the design

### 14.3.1 Introduction

In the following, the statistical model and prior distributions for the Bayesian Cox proportional hazard (PH) model will be described. We consider here the use of historical data of the same patient population (with moderately differentiated/undifferentiated, locally advanced recurrent or metastatic NPC) to enrich control arm.

#### 14.3.1.1 Model specification

The primary analysis of progression free survival (PFS) will be based on a Bayesian Cox PH model. This model will be used to estimate the hazard ratio for PFS of PDR001 vs. SOC. This model assumes that the hazard function of individual in treatment group  $i$  (PDR001 or SOC) can be expressed as;

$$\lambda_i(t) = \lambda_0(t)e^{\beta X_i}$$

Here  $\lambda_0(t)$  is the baseline hazard (or hazard for SOC),  $X_i$  indicates the treatment group membership (0 for SOC and 1 for PDR001) and  $\beta$  denotes the log hazard ratio (HR) between PDR001 group and the SOC group. Furthermore baseline or SOC group hazard function  $\lambda_0(t)$  is modeled via a piece-wise exponential model. This is a semi-parametric model which subdivides time into reasonably small  $K$  intervals and assumes that the baseline hazard is constant in each interval. i.e.,

$$\text{for } \lambda_0(t) = \lambda_{ck} \quad t \in (I_{k-1}, I_k] \quad k = 1, 2, \dots, K$$

Note that the  $\lambda_{ck}$  refer to hazard for unit time (per day). Sampling model (or likelihood) under this framework can be constructed using Binomial distribution. In this model for each of the  $K$  time intervals, the number of events in the SOC group ( $r_{ck}$ ) and PDR001 group ( $r_{Tk}$ ) follow Binomial distributions with interval-specific hazards  $\lambda_{ck}$ . Under the proportional hazards assumption it follows that

---

SOC data:	$r_{ck} \sim \text{Binomial}(n_{ck}, 1 - e^{-\lambda_{ck}L_k}),$
-----------	--

---

PDR001 data:	$r_{Tk} \sim \text{Binomial}(n_{Tk}, 1 - e^{-\lambda_{ck}e^{\beta}L_k})$
--------------	--

---

where  $n_{ck}$  and  $n_{Tk}$  are risk sets for event in the SOC and PDR001 groups, respectively, in interval  $(I_{k-1}, I_k]$  and  $L_k$  is the length of the  $k$ -th interval.

The study plans to enroll approximately 114 patients to accrue 70 events for the primary analysis of PFS endpoint. This study will be considered successful if there is sufficient evidence that the monotherapy of PDR001 is superior to SOC in PFS based on the evaluation criteria, i.e.:

- Posterior probability (HR>1) < 10%, and
- Posterior mean HR<0.7.

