### 10.4.2 Statistical hypothesis, model, and method of analysis

Patients are randomized in 2:1 ratio into either PDR001 arm or control arm. The primary efficacy endpoint, PFS as determined based on the central tumor assessment per RECIST v1.1, will be analyzed by study arm. Assuming proportional hazards for PFS, the following statistical hypothesis will be tested to address the primary efficacy objective:

$$H_{01}: \theta_1 \geq 1 \text{ vs. } H_{A1}: \theta_1 < 1$$

where  $\theta_1$  is the PFS hazard ratio (PDR001 arm vs control arm). The analysis to test this hypothesis will consist of a stratified log-rank test at an overall one-sided 10% level of significance. The stratification factor is disease status (locally advanced recurrent NPC vs. metastatic NPC).

As a supportive analysis, a Bayesian Cox proportional hazard (PH) model (see [Appendix 3](#)) will be used to estimate the hazard ratio for PFS between the two treatment combination arms. The final analysis will be performed when 70 events (progressive disease or death due to any cause) are observed from the study.

An evidence-based prior for the non-parametric, interval-specific hazards of the control arm in the Bayesian Cox PH model is derived using available historical PFS data from the list of the phase II studies (see [Table 1-1](#) and [Appendix 3](#)), using the meta-analytic-predictive (MAP) approach ([Neuenschwander et al 2010](#)) with the assumption of moderate/large between-trial heterogeneity. For more details about the model specification including the prior derivation and its operating characteristics please refer to [Appendix 3](#).

Based on the historical studies, the median PFS for the patients in the control arm is assumed to be 5.5 months (165 days).

The dual-criterion for success based on Bayesian Cox PH model is defined to show a positive result if there is enough evidence that monotherapy PDR001 is superior to the control with respect to the primary PFS endpoint, such that:

- Posterior probability ( $HR > 1$ )  $< 10\%$ , and
- Posterior median  $HR < 0.7$

The posterior median of the HRs along with the associated 95% two-sided credible intervals will be produced for the treatment comparison of PDR001 to the control. In addition, the posterior probability that the true HR lies in the following intervals will be produced:

- Substantial efficacy:  $[0, 0.55)$
- Moderate efficacy:  $[0.55, 0.7)$
- Slight efficacy:  $[0.7, 1)$
- No efficacy:  $[1, \infty)$

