### **10.8 Sample size calculation**

Assuming a 2:1 randomization ratio of PDR001 vs. Comparator, 70 events (PD or death) are to be observed in the randomized Phase II to provide 85% power to detect a 0.55 hazard ratio in terms of PFS (corresponding to a median PFS of 10 months in PDR001 group and 5.5 months in the Comparator group), using a log-rank test at a 1-sided significance level of 0.1.

The final primary analysis of PFS will be done using a Bayesian proportional hazard model when there are at least 70 events observed. Based on the simulation results under different scenarios (see [Appendix 3](#)), 70 events provide reasonable operating characteristics in terms of the probability of obtaining a positive result (as defined in [Section 10.4.2](#)). Using the Bayesian

Cox PH model with mixture MAP prior for the yields reasonable 1-sided type I error (0.081) assuming no efficacy (HR=1) and power (0.92) assuming substantial efficacy (HR=0.55) when current data is in alignment with historical data.

Considering a uniform recruitment time of about 14 months and a 15% drop out rate at 12 months, approximately 114 patients need to be randomized in a 2:1 ratio to the two arms in order to observe 70 events after approximately 6 months follow up (approximately 20 months after FPFV):

- 76 patients to the PDR001 arm
- 38 patients to the control arm

EAST® trial design software v5.4 is used to compute the sample size.

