**Step 4:**

Claim positive result for the Bayesian method if Posterior median HR < 0.7 and Prob (HR>1)< 0.1.

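### The Bayesian success rule uses the posterior median HR in 10.4.2 and the simulations but the posterior mean HR in 14.3.1.1; a median of about 0.68 to 0.70 passes one and fails the other

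*Protocol*

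**What the plan says.** Four places in the current protocol text bear on the rule.

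- **10.4.2** sets the criterion: "The dual-criterion for success based on Bayesian Cox PH model is defined to show a positive result". It has two conditions. The posterior probability that HR exceeds 1 must be under 10%, and the second reads "Posterior median $HR < 0.7" (the dollar sign is a typesetting mark). The same section names the posterior median HR, with a 95% credible interval, as the estimate to report.
- **14.3.1.1** keeps the first condition but gives the second as "Posterior mean HR<0.7".
- **14.3.2.2, Step 4**, which describes how the simulated trials were scored, says: "Claim positive result for the Bayesian method if Posterior median HR < 0.7 and Prob (HR>1)< 0.1".
- **10.8** justifies the event count by "the probability of obtaining a positive result (as defined in" Section 10.4.2, and quotes a type I error of 0.081 and a power of 0.92 when the control arm matches the historical data.

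The status of the Bayesian model also differs. Section 10.4.2 tests the primary hypothesis with a stratified log-rank test at one-sided 10% and introduces the Bayesian model as supportive. Sections 10.8 and 14.3.1.1 present the Bayesian model as the primary analysis of PFS.

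The SAP supplied is for the final study report. Its Section 2.6.2 lists Kaplan-Meier summaries of PFS and no Bayesian analysis.

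**The concern.** Posterior mean and posterior median are different summaries. The model estimates the log hazard ratio under a nearly flat prior (normal, mean 0, SD 10), so the posterior of the HR itself is roughly log-normal and its mean lies above its median. One data set can therefore meet the rule in 10.4.2 and miss the rule in 14.3.1.1.

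The line concerns a decision threshold. An analyst who programs from the model-specification section would apply a rule with no reported operating characteristics. In a borderline result, the choice between two printed rules could be made after the data are seen, which is what a pre-specified criterion is meant to prevent.

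**Working it through.** **Inputs.** From 10.8: 70 events, 2:1 allocation, HR 0.55, one-sided 0.10, 85% power. From Appendix 3: normal prior with mean 0 and SD 10 for the log HR, and a 50/50 mixture of the MAP and weakly informative priors for the control hazards.

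**1. The plan's own figure.** Schoenfeld events = (1.2816 + 1.0364)² / [(2/3)(1/3)(ln 0.55)²] = 5.373 / 0.0794 = 67.65, so 68. With 70 events the power is 0.859. The stated 70 events and 85% power reproduce.

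**2. Spread of the log HR, from the 70 events alone.** s = sqrt(1 / (70 × 2/9)) = sqrt(4.5/70) = 0.2535.

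**3. Mean against median.** For a log-normal posterior, mean = median × exp(s²/2) = median × exp(0.0321) = median × 1.033. A mean below 0.7 therefore needs a median below 0.7/1.033 = 0.678.

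**4. The other condition.** P(HR>1) < 10% needs a median below exp(−1.2816 × 0.2535) = 0.723. At this s the 0.7 threshold is the binding half, and a median from 0.678 to just under 0.70 passes 10.4.2 and fails 14.3.1.1.

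**5. Probability of success, no borrowing.** Φ[(ln c − ln HR)/s], with c = 0.70 for the median rule and c = 0.678 for the mean rule:

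| True HR | Median rule | Mean rule | Difference |
|---|---|---|---|
| 0.55 | 0.829 | 0.795 | 3.4 points |
| 0.67 | 0.569 | 0.518 | 5.0 points |
| 1 | 0.080 | 0.063 | 1.7 points |

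**6. Dependence on s.** The control prior changes the posterior SD, so a range is shown. The same s is used for the posterior and for the sampling spread.

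| s | Median needed for mean < 0.7 | Median needed for P(HR>1) < 10% | Difference at HR 0.55 / 0.67 / 1 (points) |
|---|---|---|---|
| 0.15 | 0.692 | 0.825 | 0.9 / 2.9 / 0.2 |
| 0.20 | 0.686 | 0.774 | 2.1 / 3.9 / 0.7 |
| 0.2535 | 0.678 | 0.723 | 3.4 / 5.0 / 1.7 |
| 0.30 | 0.669 | 0.681 | 1.8 / 2.3 / 1.0 |

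Above s of about 0.28 (−ln 0.7 / 1.2816) the probability condition takes over as the binding half of the median rule. At s = 0.30 the discordant band is 0.669 to 0.681.

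**7. With the mixture prior.** Two approximate simulations of the Appendix 3 model were made. One (2,000 trials per scenario) put discordance between the rules at 1.3% to 3.7% of trials. The other (800 per scenario) gave 1.6%, 1.4%, 3.5%, 2.9%, 1.0% and 3.5% for scenarios 1 to 6. In the second, the average posterior SD was about 0.23 and the mean rule was always the one that failed. One simulated trial had median 0.691, mean 0.709 and P(HR>1) 0.050.

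These figures are indicative only. The second simulation did not match Table 14-10 under the median rule: 0.126 against 0.081 in scenario 1, 0.952 against 0.922 in scenario 2, and 0.746 against 0.727 in scenario 3. The protocol does not print the censoring rate, how the mixture acts across intervals, or the correlation in the MAP prior. The simulation assumed 15% dropout at 12 months and an independent mixture in each interval. For scenario 6 it used 7.5/0.67 = 11.2 months rather than the printed 12.9.

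**The case against.** The strongest reply is that the intended rule can be recovered. Section 10.4.2 defines the criterion with the median and reports the median, Step 4 scores trials with the median, and 10.8 points to 10.4.2. One line in an appendix is the outlier. That stands, and it decides which way the correction should go.

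Three stronger readings are tempting, and the documents do not support them.

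- *The false-positive rate is compromised.* The mean rule is the stricter one, so whatever passes it also passes the median rule, and no reversal was seen in the simulation where this was counted. Type I error under the mean rule therefore cannot exceed that under the median rule. What is lost is a little power.
- *The choice of summary decides the trial's primary conclusion.* Section 10.4.2 gives the primary hypothesis test to the stratified log-rank test. Sections 10.8 and 14.3.1.1 disagree, so the weight of this point depends on how that separate contradiction is settled.
- *Table 14-10 is wrong.* It is described as produced under the median rule. The mismatch in step 7 cannot show otherwise, because needed simulation inputs are not printed.

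Practical impact is now small. SAP Section 2.2.3 says that the primary efficacy analysis in the interim report was not statistically significant, and nothing in the SAP's remaining analyses uses the rule.

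**Conclusion.** The inconsistency is real and stands in current protocol text; neither document reconciles it. A posterior median of about 0.68 to 0.70 meets one printed rule and fails the other. The shift in success probability is about 2 to 5 points in the no-borrowing approximation at 70 events, and roughly 1% to 4% of trials are discordant in approximate simulations with the mixture prior. The first figure rests on a log-normal posterior with s = 0.2535. The second rests on assumed simulation inputs and should be read as an order of magnitude.

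The quoted 0.081 and 0.92 belong to the median rule as the plan describes it; no operating characteristics are given for the mean rule. The point rates as a minor to moderate correction. It concerns a stated decision threshold, so it is more than clerical, but the band is narrow, the error is conservative, and the final analysis plan no longer applies the criterion.

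**What to change.** In 14.3.1.1, change mean to median in the line "Posterior mean HR<0.7", so that it agrees with 10.4.2 and Step 4. Confirm from the simulation code that the median was the summary used. The cost is one word and one check, and nothing needs rerunning if the code used the median.

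If the mean was intended, change 10.4.2 and Step 4, rerun Table 14-10 and update the figures quoted in 10.8.

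In the same edit, state once whether the Bayesian model is the primary or a supportive analysis of PFS, and make 10.4.2, 10.8 and 14.3.1.1 agree.

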### 14.3.1.2 Prior distribution

The Bayesian approach requires the specification of prior distributions for the model parameters. In this section we illustrated the specification of informative prior for interval specific hazards ( $\lambda_k$ 's) using relevant data for SOC from publications and non-informative prior for log hazard ratio ( $\beta$ ).

#### 14.3.1.2.1 Prior for log hazard ratio ( $\beta$ )

The prior distribution for the log hazard ratio  $\beta$  was assumed non-informative,  $\beta \sim N(\text{mean}=0, \text{sd}=10)$ .

#### 14.3.1.2.2 Prior derivation for interval specific hazard ( $\lambda_k$ 's)

A robust mixture prior will be used for interval specific hazards ( $\lambda_k$ 's). An evidence-based prior for the interval-specific hazards of the controls in the Bayesian Cox PH model is derived using a robust meta-analytic-predictive (MAP) approach ([Neuenschwander et al 2010](#); [Schmidli et al 2014](#)). The robust prior is a mixture prior with two components. The first component, derived from historical data, is a meta-analytic-predictive (MAP) prior (MAP component). The second component of the mixture prior (Weakly informative component) ensures further robustness against prior-data conflict to the control in the current trial.

- MAP component: Obtained from the published Kaplan Meier (KM) curves of 7 published studies using the meta-analytic predictive (MAP) approach.
- Weakly informative component: Reflecting the historical hazard rate for the controls but allowing for considerable prior uncertainty to handle possible prior-data conflict to the control arm in the current trial.

Further details are provided below.

#### MAP component

PFS data for SOC from 7 published studies were used to derive prior for interval specific hazards using MAP approach ([Neuenschwander et al 2010](#)). [Table 14-7](#) provides the historical data from the 7 studies of SOC treated in a total of 212 patients. These 7 trials were chosen from the 11 historical studies listed in [Table 1-1](#) of the study protocol for deriving the MAP prior. The other 6 trials were not used since the KM plots (estimates) were not available as required by the MAP approach.

**Table 14-7 Historical PFS data from 7 studies**

[Chua et al \(2003\).](#)

Time (days)	Prob. of remaining progression free	# patients at risk	# patients censored	# events
0	1	17		
30	0.76	13	0	4
60	0.70	12	0	1
90	0.64	11	0	1
120	0.59	10	0	1
150	0.47	8	0	2
180	0.35	6	0	2
240	0.21	4	0	2
300	0.21	4	0	0
360	0.21	4	0	0

[Foo et al \(2002\).](#)

Time (days)	Prob. of remaining progression free	# patients at risk	# patients censored	# events
0	1	27		
30	0.96	26	0	1
60	0.88	24	0	2
90	0.85	23	0	1
120	0.77	21	0	2
150	0.53	14	0	7
180	0.39	10	0	4
240	0.28	8	0	2
300	0.12	3	1	4
360	0.12	3	0	0

[Ngeow et al \(2011\).](#)

Time (days)	Prob. of remaining progression free	# patients at risk	# patients censored	# events
0	1	30		
30	0.96	29	0	1
60	0.67	20	0	9
90	0.64	19	0	1
120	0.53	16	0	3
150	0.50	15	0	1
180	0.40	12	0	3
240	0.11	3	0	9
300	0.07	2	0	1
360	0	0	0	2

[Peng et al \(2013\).](#)

Time (days)	Prob. of remaining progression free	# patients at risk	# patients censored	# events
0	1	48		
30	1	48	0	0
60	1	48	0	0
90	0.98	47	0	1
120	0.88	42	0	5
150	0.77	37	0	5
180	0.38	18	0	19
240	0.03	1	0	17
300	0.03	1	0	0
360	0.03	1	0	0

[Poon et al \(2005\).](#)

Time (days)	Prob. of remaining progression free	# patients at risk	# patients censored	# events
0	1	28		
30	1	28	0	0
60	0.58	16	0	12
90	0.53	15	0	1
120	0.40	11	0	4
150	0.26	7	0	4
180	0.11	3	0	4
240	0.11	3	0	0
300	0.05	2	0	1
360	0.003	0	1	1

[Wang et al \(2006\).](#)

Time (days)	Prob. of remaining progression free	# patients at risk	# patients censored	# events
0	1	39		
30	0.95	37	0	2
60	0.85	33	0	4
90	0.80	31	0	2
120	0.69	27	0	4
150	0.56	22	0	5
180	0.46	18	0	4
240	0.38	15	0	3
300	0.28	11	0	4
360	0.18	7	0	4

[Zhang et al \(2008\).](#)

Time (days)	Prob. of remaining progression free	# patients at risk	# patients censored	# events
0	1	32		
30	0.99	32	0	0
60	0.79	25	1	6
90	0.66	21	0	4
120	0.52	17	0	4
150	0.52	17	0	0
180	0.37	12	0	5
240	0.15	5	0	7
300	0.07	2	0	3
360	0.01	0	0	2

In each of the 9 time intervals of the 7 historical trials, the number of events in the SOC group follows a Binomial distribution with interval-specific SOC hazards  $\lambda_{hCk}$   $h=1,2,\dots,7$  (as stated in previous section):

Historical SOC data:  $r_{hCk} \sim \text{Binomial}(n_{hCk}, 1 - e^{-\lambda_{hCk}L_k})$ ,

The meta-analytic-predictive prior for the log-hazards  $\log(\lambda^*_{Ck})$  of the SOC arm in the current trial is obtained by analyzing the historical SOC data and using predictive distribution. The key assumption of this approach is similarity (not equality) of time-specific hazards in historical and current studies,  $\lambda_{hCk}$  and  $\lambda^*_{Ck}$ ,  $h=1,\dots,7$  and  $k=1,\dots,9$ . The degree of similarity is formally expressed via exchangeability ([Spiegelhalter 2004](#)) i.e.

$\log(\lambda_{1Ck}), \dots, \log(\lambda_{7Ck}), \log(\lambda^*_{Ck}) \sim \text{Normal}(\mu_k, \tau^2)$ .

with population mean  $\mu_k$  and between-trial standard deviation  $\tau$  for the log-hazards for the  $k$ -th time interval in the SOC group. After considering the clinical context such that unrealistically large values of  $\tau$  (eg.,  $> 1$ ) have small probability (eg., 5%), it was decided to assume the degree of similarity as

$$\tau \sim \text{log-normal}(\text{mean}=\log(0.5), \text{sd}=0.354)$$

This prior distribution has median 0.5, which amounts to moderate to large heterogeneity, and 95% probability interval (0.25,1.00), which covers a range of moderate to large heterogeneity ([Spiegelhalter et al 2003](#)).

Moreover in order to explore the related structure we modeled each  $\mu_k$  by relating to neighboring by a  $\mu_{k-1}$  linear model. The model assumes the following functional form

$$\begin{aligned} \mu_k &\sim N(\eta_k, \sigma^2_{\kappa}) \\ \eta_k &= \eta_{k-1} + \rho_{k-1} \quad k=2, 3, \dots, 9 \end{aligned}$$

Prior for  $\eta_1$  is assumed to be  $N(\text{mean}=-1.386, \text{sd}=0.353)$  and  $\rho_{k-1} \sim N(\text{mean}=0, \text{sd}=1)$ , and  $\sigma^2_{\kappa} = \omega * 0.353^2$  with  $\omega \sim \text{Uniform}(0,1)$ . This uses similar formulation as [Krams et al \(2005\)](#).

As mathematical closed form are not tractable statistical inference for the log-hazards of the SOC group in the new trial,  $\log(\lambda^*_{Ck})$ , was obtained using WinBUGS. Note that for PFS times

[figure not shown]
that exceed 360 days (the maximum time in the historical data set), the prior for these log-hazards is assumed equal mean to the prior from the last available log-hazard, i.e.,  $\lambda^*_{C9}$  but greater standard deviation. [Table 14-8](#) displays the prior summaries of the log-hazards (per day).

**Table 14-8** Prior distribution of daily long-hazards

Time interval (days)	Log-hazards	
	Mean	SD
1-30	-6.771	0.560
31-60	-5.245	0.484
61-90	-6.202	0.538
91-120	-5.376	0.501
121-150	-5.206	0.494
151-180	-4.298	0.479
181-240	-4.399	0.480
241-300	-5.055	0.531
301-360	-4.752	0.571
360-420	-4.752	1.151
420-480	-4.752	2.080
480-540	-4.752	3.054

Figure 14-1 shows the prior progression free survival probabilities and 95% credible interval (dotted line). This shows that the prior median is around 5.5 months.

**Figure 14-1 Prior distribution of corresponding progression free survival probabilities**

### Weakly informative component

When considering the use of historical controls in the current trial, a careful selection of the historical trials is necessary to render the exchangeability assumption for the SOC parameters plausible. Nevertheless, one has to acknowledge the possibility of prior-data conflict. Hence, we consider a robust version of the MAP prior by assuming a weakly informative prior for  $\log(\lambda_{CK})$  as  $N(\text{mean}=-6.771, \text{sd}=3)$ . This allows to take into account the additional uncertainties.

### Mixture prior

To obtain the mixture prior, 50% weight will be assigned to the MAP component, and 50% weight will be assigned to the weakly informative component to be more on conservative side to handle possible prior data conflict.

### 14.3.2 Operating characteristics

The purpose of this section is to present the operating characteristics of the proposed design under various scenarios. The data for the SOC arm are simulated such that for some scenarios they are in alignment with the historical control data and for the others, they are not. Different magnitudes of efficacy are also considered, e.g, no efficacy, moderate efficacy and substantial efficacy under different scenarios. Type I error rate and power for this design under different scenarios will be investigated as mentioned in details in the next section.

#### 14.3.2.1 Scenarios investigated

In order to investigate the operating characteristics, data are simulated under the scenarios as described in [Table 14-9](#).

**Table 14-9 Different scenarios of operating characteristics simulations**

Scenario#	Current control aligned with prior?	Efficacy Magnitude	Median PFS, SOC arm (months)	Median PFS, PDR001 arm (months)	True Hazard Ratio
1	Yes	No efficacy	5.5	5.5	1
2	Yes	Substantial	5.5	10.0	0.55
3	Yes	Moderate	5.5	8.2	0.67
4	No	No efficacy	7.5	7.5	1
5	No	Substantial	7.5	13.6	0.55
6	No	Moderate	7.5	12.9	0.67

As shown in the [Table 14-9](#), SOC data are simulated to be aligned with the prior for scenarios 1-3. Different magnitudes of efficacy will be tested in these three scenarios by varying the true hazard ratio. For scenario 1, hazard ratio 1 means that there is no efficacy. The simulation output in this case provides Type I error rate. For the other two scenarios, powers are obtained. Similarly for scenarios 4-6, controlled data not aligned with prior are simulated and scenario 4 is the case with no efficacy where the simulation results provides Type I error rate.

